## Ethical and Regulatory Requirements

The principles for ethical and regulatory requirements for the study, including this genetics research component, are outlined in Section 7 of the protocol.

## Informed Consent

The genetic component of this study is optional, and the subject may participate in other components of the main study without participating in the genetic component. To participate in the genetic component of the study the subject must sign and date both the consent form for the main study and the genetic component of the study. Copies of both signed and dated consent forms must be given to the subject and the originals filed at the study center. The Principal Investigator(s) is responsible for ensuring that consent is given freely and that the

subject understands that they may freely discontinue from the genetic aspect of the study at any time.

### **Subject Data Protection**

MedImmune will not provide individual genotype results to subjects, any insurance company, any employer, their family members, or their general physician unless required to do so by law.

Extra precautions are taken to preserve confidentiality and prevent genetic data being linked to the identity of the subject. In exceptional circumstances, however, certain individuals might see both the genetic data and the personal identifiers of a subject. For example, in the case of a medical emergency, a MedImmune Physician or an investigator might know a subject's identity and also have access to his or her genetic data. Also, Regulatory authorities may require access to the relevant files, though the subject's medical information and the genetic files would remain physically separate.

### **Data Management**

Any genotype data generated in this study will be stored at a secure system at MedImmune and/or designated organizations to analyze the samples.

The results from this genetic research may be reported in a separate report from the CSR or published in scientific journals.

MedImmune and its designated organizations may share summary results (such as genetic differences from groups of individuals with a disease) from this genetic research with other researchers, such as hospitals, academic organizations or health insurance companies. This can be done by placing the results in scientific databases, where they can be combined with the results of similar studies to learn even more about health and disease. The researchers can only use this information for health-related research purposes. Researchers may see summary results, but they will not be able to see individual subject data or any personal identifiers.

Some or all of the clinical datasets from the main study may be merged with the genetic data in a suitable secure environment separate from the clinical database.

### **Statistical Methods and Determination of Sample Size**

The number of subjects who will agree to participate in the genetic research is unknown. It is therefore not possible to establish whether sufficient data will be collected to allow a formal statistical evaluation or whether only descriptive statistics will be generated. A Statistical Analysis Plan will be prepared where appropriate.

## Appendix F Response Evaluation Criteria in Solid Tumors Version 1.1

### F 1 Measurability of Tumor Lesions

Tumor lesions will be categorized as follows:

- **Measurable Lesions** - Must be accurately measured in at least one dimension (longest diameter in the plane of measurement is to be recorded) with a minimum size of:
  - 10 mm by CT scan (irrespective of scanner type) and MRI (no less than double the slice thickness and a minimum of 10 mm).
  - 10 mm caliper measurement by clinical examination (when superficial).
  - Malignant lymph nodes are considered pathologically enlarged and measurable, a lymph node must be  $\geq 15$  mm in short axis when assessed by CT scan (CT scan slice thickness recommended to be no greater than 5 mm).
- **Nonmeasurable Lesions** - Nonmeasurable lesions are defined as all other lesions (or sites of disease), including small lesions (longest diameter  $< 10$  mm or pathological lymph nodes with  $\geq 10$  to  $< 15$  mm short axis). Lesions considered truly nonmeasurable include the following: leptomeningeal disease, ascites, pleural/pericardial effusion, inflammatory breast disease, lymphangitic involvement of skin or lung, and abdominal masses/abdominal organomegaly identified by physical examination that is not measurable by reproducible imaging techniques.
- **Target Lesions** - At baseline, all lesions up to a maximum of 5 lesions total (and a maximum of 2 lesions per organ) representative of all involved organs should be identified as target lesions. It may be the case that, on occasion, the largest lesion does not lend itself to reproducible measurement in which circumstance the next largest lesion which can be measured reproducibly should be selected.
- **Non-target Lesions** - It is possible to record multiple non-target lesions involving the same organ as a single item (eg, “multiple enlarged pelvic lymph nodes” or “multiple liver metastases”).
- **New Lesions** - Though only certain new lesion measurements will be included in the tumor burden, all new lesions that can be accurately measured should be recorded. Up to 5 additional target lesions (maximum of 2 additional lesions per organ) may be added to the tumor burden at each postbaseline assessment to facilitate the exploratory iRECIST analysis. Other new lesions will be included into the non-tumor burden.

## F 2 RECIST v1.1 Response Criteria

### Evaluation of Target Lesions

- **CR** - Disappearance of all target lesions. Any pathological lymph nodes (whether target or non-target) must have reduction in short axis to < 10 mm (the sum may not be “0” if there are target nodes).
- **PR** - At least a 30% decrease in the sum of the diameters of target lesions, taking as reference the baseline sum diameters.
- **PD** - At least a 20% increase in the sum of diameters of target lesions, taking as reference the smallest sum on study (this includes the baseline sum if that is the smallest on study). In addition to the relative increase of 20%, the sum must also demonstrate an absolute increase of at least 5 mm. (Note: the appearance of one or more new lesions is also considered PD.)
- **SD** - Neither sufficient shrinkage to qualify for PR nor sufficient increase to qualify for PD, taking as reference the smallest sum of diameters while on study.

### Evaluation of Non-target Lesions

- **CR** - Disappearance of all non-target lesions and normalization of tumor marker level. All lymph nodes must be non-pathological in size (< 10 mm short axis).
- **Non-CR/Non-PD** - Persistence of 1 or more non-target lesion(s) and/or maintenance of tumor marker level above the normal limits.
- **PD** - Unequivocal progression of existing non-target lesions will be defined as the overall level of substantial worsening in non-target disease such that, even in presence of SD or PR in target disease, the overall tumor burden has increased sufficiently to merit discontinuation of therapy (see Section 4.1.6). In the absence of measurable disease, change in non-measurable disease comparable in magnitude to the increase would be required to declare PD for measurable disease. Examples include an increase in a pleural effusion from ‘trace’ to ‘large,’ an increase in lymphangitic disease from localized to widespread.

### Appearance of New Lesions

The appearance of new lesions is considered PD according to RECIST v1.1. Considering the unique response kinetics that have been observed with immunotherapy, new lesions can nonetheless derive clinical benefit.

### Evaluation of Overall Response

For the overall response based on RECIST v1.1, confirmation of CR and PR is required by a repeat, consecutive assessment no less than 4 weeks from the date of first documentation. If a subject discontinues the study due to PD and begins another treatment, a confirmatory scan is not required.

**Table F1** provides overall responses for all possible combinations of tumor responses in target and non-target lesions with or without the appearance of new lesions.

**Table F1 Evaluation of Overall Response Using RECIST v1.1**

| Target Lesions                | Non-target Lesions   | New Lesions | Overall Response                                |
|-------------------------------|--|-------------|---|
| Complete response             | Complete response (or no non-target lesion)                                      | No          | Complete response                               |
| No target lesion a | Complete response  | No          | Complete response                               |
| Complete response             | Not evaluable b   | No          | Partial response                                |
| Complete response             | Non-complete response / non-progressive disease                                  | No          | Partial response                                |
| Partial response              | Non-progressive disease and not evaluable (or no non-target lesion) b | No          | Partial response                                |
| Stable disease                | Non-progressive disease and not evaluable (or no non-target lesion) b | No          | Stable disease                                  |
| Not all evaluated             | Non-progressive disease  | No          | Not evaluable                                   |
| No target lesion a | Not all evaluated  | No          | Not evaluable                                   |
| No target lesion a | Non-complete response / non-progressive disease                                  | No          | Non-complete response / non-progressive disease |
| Progressive disease           | Any  | Yes/No      | Progressive disease                             |
| Any                           | Progressive disease  | Yes/No      | Progressive disease                             |
| Any                           | Any  | Yes         | Progressive disease                             |
| No target lesion a | Unequivocal progressive disease  | Yes/No      | Progressive disease                             |
| No target lesion a | Any  | Yes         | Progressive disease                             |

RECIST v1.1 = Response Evaluated Criteria in Solid Tumors version 1.1.

a Defined as no target lesion at baseline.

b Not evaluable is defined as either when no or only a subset of lesion measurements are made at an assessment.

Reference: [Eisenhauer et al, 2009](#)

CCI

CCI

CCI

CCI

CCI

|  |  |  |
|--|--|--|
|  |  |  |
|  |  |  |
|  |  |  |
|  |  |  |
|  |  |  |
|  |  |  |
|  |  |  |
|  |  |  |
|  |  |  |

CCI

CCD

A 5x3 grid of binary images, likely representing brain scans. The first two columns are labeled 'CCI' in red text. The images show various brain structures in black on a white background. The 'CCI' label appears in red text in the first two columns of the grid.

## List of Abbreviations

Abbreviation or Specialized Term	Definition
AE	adverse event
ATC	Anatomical Therapeutic Chemical
BICR	Blinded Independent Central Review
BMI	body mass index
C Cr	creatinine clearance rate
CRF	case report form
CCI	CCI
cCRT	concurrent chemoradiotherapy
CR	complete response
DoR	duration of response
DA	disease assessment
DC	disease control
DCO	data cutoff
DCR	disease control rate
eCRF	electronic Case Report Form
ECG	electrocardiogram
ECOG	Eastern Cooperative Oncology Group
GFR	glomerular filtration rate
HR	hazard ratio
CCI pd	CCI
CCI	CCI
Ig	immunoglobulin
IHC	immunohistochemistry
IP	investigational product
IPD	important protocol deviation
ITT	Intent-to-treat
IV	intravenous
IxRS	interactive voice/web response system
LLOQ	lower limit of quantification
MedDRA	Medical Dictionary for Regulatory Activities
CCI	CCI
LRV	lower reference value
NSCLC	non-small cell lung cancer
OR	objective response

Abbreviation or Specialized Term	Definition
ORR	objective response rate
OS	overall survival
OS-12 (18, 24, 36)	overall survival at 12 (18, 24, 36) months
PD	progressive disease
PFS	progression-free survival
PFS-12 (18, 24, 36)	progression-free survival at 12 (18, 24, 36) months
PK	pharmacokinetics
PR	partial response
RECIST	Response Evaluation Criteria in Solid Tumors
SAE	serious adverse event
SC	subcutaneous
SD	stable disease
SPP	statistical programming plan
TFL	Tables, figures, listings
CCI	CCI
TV	target value

## 1 INTRODUCTION

This document describes the statistical analysis methodology for protocol D9108C00001, a multidrug platform study of Durvalumab (MEDI4736) alone or in combination with novel agents in subjects with locally advanced, unresectable, stage III non-small cell lung cancer (NSCLC). As background information, an overview of the study design is provided. The main portion of this document details the statistical summaries relating to each study objective and describes the general conventions and definitions that will be used. In addition, a set of table templates and specifications will be included in a statistical programming plan (SPP) to complement this document.

## 2 STUDY OVERVIEW

### 2.1 Study Objectives

#### 2.1.1 Primary Study Objective(s)

To compare the antitumor activity of durvalumab alone vs. durvalumab in combination with novel agents.

#### 2.1.2 Secondary Study Objectives

Safety:

- To evaluate the safety and tolerability of durvalumab alone and durvalumab in combination with novel agents.

Clinical activity:

- To further compare the efficacy of durvalumab alone vs durvalumab in combination with novel agents.

Pharmacokinetics (PK):

- To describe the PK of durvalumab alone and durvalumab in combination with novel agents.
- To describe the PK of novel agents in combination with durvalumab.

Immunogenicity:

- To assess the immunogenicity of durvalumab alone or in combination with novel agents.
- To assess the immunogenicity of novel biologic agents in combination with durvalumab.

### 2.1.3 Exploratory Study Objectives

CCI

Term	Percentage
GMOs	95
Organic	90
Natural	85
Artificial	75
Organic	90
Natural	85
Artificial	75
Organic	90
Natural	85
Artificial	75
Organic	90
Natural	85
Artificial	75

## 2.2 Study Design

COAST is a Phase 2, open-label, multicenter, randomized, multidrug platform study of durvalumab alone or in combination with novel agents in subjects with locally advanced, unresectable, Stage III NSCLC.

The study will evaluate the clinical activity and safety of durvalumab alone or in combination with novel agents in subjects with Stage III NSCLC who have not progressed following definitive concurrent chemoradiotherapy (cCRT) (Figure 1 in protocol). Subjects will be

randomized into the study and initiate study treatment within 42 days from the last session of cCRT. Up to approximately 80 sites globally will participate in this study.

Subjects may be treated for up to 12 months. Study treatment will be discontinued upon confirmed disease progression, unacceptable toxicity, or other reasons, e.g., subject decision or noncompliance with study procedures. Overall, all subjects continuing in the study must adhere to the study procedures for up to 5 years (from randomization) provided they achieve disease control (DC) and remain disease free.

After completing the 5-year post-randomization study period, all subjects included into any treatment arm may be contacted annually for survival until 5 years after the final subject is randomized into the study or until the sponsor stops the study, whichever occurs first. The platform nature of the study allows an experimental arm to be permanently closed while the overall COAST study remains open.

New durvalumab combination experimental arms may be added based on emerging non-clinical and clinical data via protocol amendment. Interim futility analyses will be performed using Bayesian predictive probability.

Details about treatment regimen can be found in Section 3.1.2 of the protocol.

## 2.3 Treatment Assignment and Blinding

### Treatment Assignment

An interactive voice/web response system (IxRS) will be used to assign investigational product (IP) kit numbers to each subject who meets the eligibility criteria. A randomization method with dynamically changing randomization ratios will be employed to account for fluctuation in the number of treatment arms open for enrollment over the course of the study. The randomization will be stratified by histology (adenocarcinoma vs non-adenocarcinoma) and will use an equal ratio to all study treatment arms open for enrollment (e.g., if experimental arms are opened sequentially, an experimental arm is added/closed, or enrollment in an experimental arm is suspended). Additionally, the following considerations regarding randomization will apply:

- If there is no experimental arm open for enrollment, then enrollment will be paused. Any subject who had consented previously and was in screening when the experimental arm(s) was closed due to safety concerns may be allowed to enter into the study but must be allocated to the control arm.

- Once the control arm enrolls 60 subjects, a subsequent randomization scheme may be initiated to optimize the number of subjects allocated to control arm.
- At any point during the study, the control arm will have no less than a 33% chance to be randomized in comparison to the active experimental arm that has the lowest randomization ratio in the study.

### **Blinding**

The study is not blinded.

### **2.4 Sample Size**

Sixty subjects will be enrolled in each of the combination therapy experimental arms and more than 60 subjects will be enrolled in the durvalumab control arm dependent upon the length of the study. The sample size of 60 subjects per experimental arm is not designed to make explicit power and Type I error considerations for a hypothesis test. It is primarily chosen to obtain a preliminary assessment of antitumor activity with a certain degree of precision.

Table 2.4-1 shows estimated differences in objective response rate (ORR) between an experimental arm and control arm along with 2-sided 95% exact CIs with a sample size of 60 subjects each. Sixty subjects per treatment arm provides a 95% CI with reasonable width (approximately  $\pm 18\%$ ) for the estimated ORR difference between a durvalumab combination experimental arm and the durvalumab control arm. For a 20% increase in ORR in any durvalumab combination experimental arm over durvalumab control arm (50% vs 30%, respectively), the lower limit of the 95% CI for the difference between these arms is 1%, which is greater than 0%, suggesting that the durvalumab combination experimental arm will have a higher ORR than the durvalumab control arm with 95% confidence.

**Table 2.4-1      Estimated Differences in ORR Between Experimental and Control Arm of 60 Subjects Each**

Number of Responders (ORR)		Difference (%) in ORR (2-sided 95% Exact Confidence Interval)
Experimental Arm (n = 60)	Control Arm (n = 60)	
24 (40%)	18 (30%)	10% (-9%, 28%)
27 (45%)	18 (30%)	15% (-4%, 33%)
30 (50%)	18 (30%)	20% (1%, 38%)
33 (55%)	18 (30%)	25% (6%, 42%)

ORR = objective response rate.

### 3 STATISTICAL METHODS

#### 3.1 General Considerations

Tabular summaries will be presented by treatment group. Categorical data will be summarized by frequency distribution (number and percentage of subjects falling within each category). Continuous variables will be summarized by descriptive statistics including N, mean, standard deviation, median, and range (minimum and maximum). All available data will be used, and thus missing data will not be imputed, unless otherwise specified. In general, subjects with missing data for a parameter will be excluded from the summary of this parameter. Tables will be supported by data listings showing the original data forming the basis for the summaries. Data listings will be sorted by treatment group, subject number and date collected where applicable.

Unless stated otherwise, two-sided confidence intervals will be produced at 95%. Baseline values will be defined as the last valid assessment prior to the first administration of IP. Assessments on the day of the first dose where neither time nor a nominal pre-dose indicator are captured are considered prior to the first dose if such procedures are required by the protocol to be conducted before the first dose.

Data analyses will be conducted using the SAS® System (SAS Institute, Inc., Cary, NC, USA) Version 9.4 or above, unless otherwise specified. All analysis outputs will be validated according to MedImmune SAS programming standards and MedImmune validation procedures.

#### 3.2 Analysis Populations

The analysis populations are defined in [Table 3.2-1](#).

**Table 3.2-1      Analysis Populations**

Population	Description
Intent-to-treat (ITT) Population	The ITT population includes subjects who are randomized. Subjects will be analyzed according to their randomized treatment group.
As-treated Population	The As-treated population includes all subjects who receive any IP. Subjects will be analyzed according to the treatment they really receive.
Response-evaluable Population	The Response-evaluable population includes subjects from the As-treated population who have a baseline disease assessment (DA), have the opportunity to be followed for at least 16 weeks at the time of the DCO (i.e., dosed at least 16 weeks prior to the time of the DCO), and either has at least one post-baseline disease assessment and/or discontinued treatment due to death or disease progression. The response-evaluable population will not be used for the final analysis.

**Table 3.2-1      Analysis Populations**

Population	Description
PK-evaluable Population	The PK-evaluable population includes subjects from the As-treated population who have a non-missing baseline PK concentration and at least one non-missing post-baseline PK concentration.

IP = investigational product; PK = pharmacokinetic.

All baseline and efficacy parameters will be summarized based on the ITT population as primary analysis. The efficacy parameters may be summarized based on response-evaluable population as supportive analysis. Safety parameters will be summarized based on the As-treated population as primary analysis. The analysis of pharmacokinetics will be based on the PK-evaluable population.

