### 4.3.4 Pharmacokinetic Evaluation and Methods

Blood samples will be collected to evaluate PK in serum of durvalumab when administered alone or in combination with novel agents. Additionally, PK in serum of novel agents administered in combination with durvalumab will be evaluated. Novel agents include oleclumab and monalizumab. See Section 4.2 for collection time points. Evaluations will be performed using a validated immunoassay.

In combination arms, at visits when predose and end of infusion (EOI) samples are required, PK predose (within 1 hour prior to dosing) and EOI (within 15 minutes post-EOI) samples will be collected according to the administration time of each study drug. For example:

PK predose Agent 1 collected → Agent 1 administration → PK EOI Agent 1 collected → PK predose Agent 2 collected → Agent 2 administration → PK EOI Agent 2 collected.

In combination arms, at visits when predose samples only are required, PK samples will be collected within 1 hour prior to administration of the first study drug only. For example: PK predose Agent 1 and Agent 2 collected → Agent 1 administration → Agent 2 administration.

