### **Pharmacokinetics**

Only subjects who receive at least 1 dose of durvalumab and/or other combination study drug, and provide at least 1 post-treatment sample, will be evaluated. For each treatment arm, individual durvalumab concentrations will be tabulated with descriptive statistics. Additionally, for each experimental arm, individual novel agent concentrations will be tabulated with descriptive statistics.

Non-compartmental PK data analysis will be performed from each treatment arm with scheduled PK sample collection where data allow. Relevant descriptive statistics of non-compartmental PK parameters will be provided and may include: area under the concentration-time curve, observed maximum concentration, clearance, and terminal half-life.

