### 3.8 Pharmacokinetics

For each treatment group in the PK-evaluable population, serum concentrations of the study drug will be summarized by visit/timepoint with descriptive statistics. Individual novel agent concentrations will be summarized similarly. Serum concentrations will be reported in ug/mL, and the lower limit of quantification (LLOQ) for each analyte will be defined in the SPP. The following statistics are presented: n, n below LLOQ, geometric mean, geometric coefficient of variation (%), arithmetic mean, standard deviation, coefficient of variation (%), median, minimum, and maximum.

More details about calculations can be found in the SPP. All serum concentration data will be listed for each subject, by analyte.

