5.0	04SEP2023	
 
1. Added a few terms in the list of abbreviations
 
2. Section 3.1 clarified for the definition of baseline
 
3. Updated SAS version to 9.4
 
4. Table 3.2-1 Added PK-evaluable population
 
5. Section 3.3.3 removed data cut-off from duration of exposure definition
 
6. Section 3.3.4 add ATC and WHO Drug version
 
7. Section 3.3.5 Added COVID-19 related IPDs
 
8. Section 3.4.2.4 Added PFS-36 month landmark
 
9. Section 3.4.2.4 Updated and clarified the Greenwood's formula, and added more details
 
10. Section 3.4.2.5 Added OS-36 month landmark
 
11. Section 3.5 Updated section to clarify that no pharmacodynamic analyses are planned at this stage
 
12. Section 3.6 Added clarification regarding any derivation timeframe (in Labs, VS, ECOG)
 
13. Section 3.6.4 Updated wording to increase readiness and match what the expectations are, for the laboratory tables
 
14. Section 3.6.4 Creatinine clearance rate formula added
 
15. Section 3.6.5.1 Removed 10% subjects wording and added minimum and maximum post-baseline summaries of vital signs
 
16. Section 3.6.5.2 Added information as to why no ECG analyses are planned for the CSR
 
17. Section 3.6.5.4 Added a section for physical examinations (none planned)
 
18. Section 3.8 Added PK analysis plan
 
19. Section 3.8 Mentioned that all results to be reported in ug/mL
 
 
Other minor clarifications were made throughout.
	
 
1. Previously missing some abbreviations, and new ones corresponding to new updates
 
2. Lack of information in defining baseline when no time indicator captured
 
3. Latest SAS version available
 
4. SAP now includes PK analysis
 
5. No DCO defined in final CSR
 
6. Clarify that the summary of concomitant medications is by ATC and PT
 
7. COVID-19 related IPDs might be required for the CSR
 
8. Agreed with the team in prior communications to include PFS-18, PFS-24 and PFS-36 landmarks for the CSR
 
9. Lack of precision in the formula details (<math>n_i</math> refers to deaths or disease progressions in the PFS section, difference between <math>i</math> and <math>k</math>)
 
10. Agreed with the team in prior communications to include OS-18, OS-24, and OS-36 landmarks for the CSR
 
11. Previous version outdated (MedImmune process) - Wording confirmed with PK/PD team
 
12. Discussed during the Dry Run review with the team to consider only post-baseline visits up to and including 90 days post last dose of study drug
 
13. Wording was unclear and disorganized, clarification was needed
 
14. Information more complete with additional details provided
 
15. CSP doesn't mention a selection criterion (10% of subjects) so not needed here, but mentions min/max summaries of vital signs
 
16. CSP mentions ECG analyses while ECGs were only collected at screening
 
17. CSP mentions physical examination statistical analysis,
 

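### The SAP's PK-evaluable population adds a baseline-concentration condition that the protocol's PK evaluability rule does not contain and the planned PK summaries do not use

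*SAP*

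**What the plan says.** SAP Table 3.2-1 defines the PK-evaluable population as members of the As-treated population "who have a non-missing baseline PK concentration and at least one non-missing post-baseline PK concentration". The text under the table makes this the analysis set: "The analysis of pharmacokinetics will be based on the PK-evaluable population". SAP 3.8 applies it to the output: "For each treatment group in the PK-evaluable population, serum concentrations of the study drug will be summarized by visit/timepoint with descriptive statistics". The same section keeps the listings wider: "All serum concentration data will be listed for each subject, by analyte".

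The protocol states its rule twice, in the synopsis (Pharmacokinetics and Immunogenicity) and in Section 4.8.5. Only subjects who received at least one dose of study drug and who "provide at least 1 post-treatment sample, will be evaluated". No baseline condition appears in either place.

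The protocol does plan the sample. Table 5 schedules predose and end-of-infusion PK samples at Cycle 1, and Section 4.3.4 gives the windows: "PK predose (within 1 hour prior to dosing) and EOI (within 15 minutes post-EOI) samples will be collected". In the combination arms these are timed to each drug separately.

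SAP 3.1 sets the general baseline rule: "Baseline values will be defined as the last valid assessment prior to the first administration of IP".

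The PK-evaluable population entered at SAP version 5.0. The reason recorded in the version history is "SAP now includes PK analysis". Nothing is said about the baseline condition.

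**The concern.** The SAP set is narrower than the set the protocol describes, without a stated reason. Version 5.0 of the SAP does record its departures from the protocol on ECG and physical examination, so the silence here suggests that this difference was not noticed.

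The added condition does no work in the planned analysis. SAP 3.8 calls for descriptive statistics of concentration at each visit and timepoint. There is no change from baseline and no baseline adjustment. An end-of-infusion or trough value can be summarised whether or not the Cycle 1 predose result exists.

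If that one result is missing, the subject's Cycle 1 end-of-infusion value and the predose values at Cycles 2, 7 and 11 leave the summaries, as does any follow-up sample. Describing PK is a secondary objective. Protocol Section 9.1 says that no subject is still receiving study treatment, so a missed predose sample cannot be replaced. Only the definition can change.

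**Working it through.** The plan gives no PK sample size, precision target or count of exclusions, so there is no figure to reproduce. The check compares the texts and adds a calculation for scale.

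**1. Conditions side by side**

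| Condition | Protocol synopsis and 4.8.5 | SAP Table 3.2-1 |
|---|---|---|
| At least one dose | Yes | Yes (through As-treated) |
| At least one post-dose result | Yes (worded as a sample) | Yes (worded as a non-missing concentration) |
| Non-missing baseline concentration | Not stated | Required |

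The third row is a restriction found only in the SAP. The SAP set is smaller whenever a dosed subject has a post-dose concentration but no baseline result.

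**2. Does the baseline definition fit the sampling scheme?**

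- SAP 3.1 counts only assessments made before the first administration of IP.
- Protocol Table 5 (footnote i) and Section 4.3.4 give the Cycle 1 order: predose sample for the first agent, first agent, its end-of-infusion sample, then predose sample for the second agent, second agent, its end-of-infusion sample.
- The second agent is durvalumab in Arm A (Figure 3 footnote: oleclumab goes first) and monalizumab in Arm B (Figure 4 footnote: durvalumab goes first).
- So the scheduled Cycle 1 predose sample for durvalumab in Arm A and for monalizumab in Arm B comes after the first administration of an IP. If IP means any study drug, that sample is not a baseline sample. If IP means the drug being assayed, it is.
- Table 3.2-1 does not say which reading applies, or whether the condition is checked per subject or per analyte.

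**3. Scale, for illustration**

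Inputs: n = 60 per arm (protocol 4.1.1, approximate, and taken here as all treated); m = proportion with a missing baseline result, not in the documents and assumed to be 1% to 10%.

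- One analyte: expected exclusions = 60 × m; chance of at least one = 1 − (1 − m)^60.
- Combination arm, if a subject is dropped when either drug's baseline is missing, with the two independent: expected exclusions = 60 × [1 − (1 − m)²].

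| m (assumed) | Expected exclusions, one analyte | Chance of at least one | Expected exclusions, either of two |
|---|---|---|---|
| 1% | 0.6 | 0.45 | 1.2 |
| 2% | 1.2 | 0.70 | 2.4 |
| 5% | 3.0 | 0.95 | 5.9 |
| 10% | 6.0 | 1.00 (0.998) | 11.4 |

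Under the protocol's rule, none of these subjects would be excluded for want of a baseline result. Losing 3 or 6 of 60 would raise the standard error of a mean by √(60/57) = 1.026 or √(60/54) = 1.054, that is, by 2.6% or 5.4%. Standard error is not among the statistics listed in SAP 3.8.

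**The case against.** The best defence is that the protocol sentence begins with the word Only. It sets a minimum: subjects without a dose or a post-treatment sample are out. It does not promise that everyone who meets it enters every summary, and protocol 4.8.1 leaves further analysis detail to the SAP. On that reading the SAP refines the rule rather than contradicts it. This is a fair reading, and it rules out saying that the protocol guarantees every such subject a place. It does not supply a reason for the refinement, and neither does the SAP.

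A predose value might be wanted for the non-compartmental analysis that protocol 4.8.5 foresees where data allow. That could justify a condition on that analysis. It would not justify one on concentration summaries by timepoint, which are what SAP 3.8 sets out.

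Several stronger readings are tempting, and the documents do not support them:

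- That the protocol plans no baseline PK sample. Table 5 schedules one at Cycle 1; it is just not a condition of evaluability.
- That data are discarded. Excluded subjects' values stay in the listings.
- That subjects have in fact been lost. No document reports a missing Cycle 1 predose result.
- That the predose value cannot carry information because nobody was previously exposed. Exclusion criterion 5 bars earlier anti-PD-1, anti-PD-L1 and anti-CTLA-4 antibodies given for NSCLC. It does not name agents against CD73 or NKG2a. A predose value below quantification is likely, but not fully documented.
- That a predose result below the LLOQ would itself exclude a subject. SAP 3.8 counts such results, so they should be non-missing, though Table 3.2-1 does not say so.
- That the second drug's summaries would be empty in the combination arms. This follows only if IP is read as any study drug and the condition is applied per analyte. Reading IP drug by drug avoids it and is probably what was meant.

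**Conclusion.** The point holds as a mismatch between SAP and protocol. The SAP makes a non-missing baseline concentration a condition of the PK analysis; the protocol's rule has no such condition, and the planned summaries do not need it. The SAP also leaves open how baseline is to be determined for the second drug in Arms A and B.

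The number of subjects affected is unknown and may be zero. The range of about 0.6 to 6 of 60 per arm rests wholly on the assumed 1% to 10% missingness and on one analyte at a time. It could be up to 11.4 of 60 if either drug's missing baseline removed the subject.

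The effect is confined to a descriptive secondary objective. Efficacy and safety use other populations, and immunogenicity is summarised on the As-treated population (SAP 3.7). No trial conclusion turns on this. It is a low-priority correction, worth making because it costs almost nothing.

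**What to change.** In SAP Table 3.2-1, define the PK-evaluable population as As-treated subjects with at least one dose and at least one non-missing post-dose concentration, applied separately for each analyte. State that a result below the LLOQ counts as non-missing. This matches the protocol's rule and removes the need to decide what baseline means for the second drug.

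If the sponsor wants to keep the baseline condition, the SAP should give the reason, record it as a departure from protocol 4.8.5, and say that baseline is judged against the first dose of the drug being assayed.

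The cost is one phrase in the SAP and the matching population flag in the programming. No new data and no protocol amendment are needed.
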